The current study aims to conduct a comprehensive evaluation of a training curriculum designed for teaching low-intensity psychological interventions to bachelor's degree holders, specifically focusing on principles of Acceptance and Commitment Therapy (ACT) and its intervention effectiveness. This evaluation is divided into two integral parts. In the first part, the curriculum, which encompasses a 120-hour intensive teaching block followed by a nine-month placement, will be evaluated. To assess the trainees' competencies in applying the principles of ACT, a series of role-play examinations will be administered at various time points, including pre-training, pre-placement, mid-placement, and end-of-placement. Focus groups will be conducted.

The second part of the evaluation is to examine the outcomes of low-intensity psychological interventions, delivered by the trainees, targeting adult individuals (age ≥ 18) screened with mild to severe symptoms of depression and anxiety. To achieve this, a series of questionnaires will be administered at several stages: pre-intervention, during each session, and at a three-month follow-up. Outcome measures will include the assessment of depressive

and anxiety symptom severity, quality of life, functional impairment, therapeutic alliance, and the level of experiential avoidance. Individual exit interviews and focus groups will be conducted.

Hypotheses

It is hypothesised that the competency level of the training participants will increase after the intensive training block and the placement. It is hypothesised that after receiving the low-intensity psychological intervention based on the Acceptance and Commitment Therapy (ACT) principle, the depression and anxiety scores, functioning impairment, and experiential avoidance level will reduce, and quality of life and therapeutic relationship will improve.

Methodology

Training Participants

Participants from the Psychological Wellbeing Practitioners (PWPs) Programme will be invited to participate in the research. The PWPs are degree holders who will undergo 120 hours of intensive training block, followed by 9 months of placement to practise the learnt skills. Given therapist competency will be part of the programme, this research will request the participants to consent to the use of the data collected in the programme.

Service Participants

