For training evaluation, given the current training programme has already consists of therapist competency assessment to ensure the quality of the training participants. A record of role-play videos will be rated the ACT therapist competency by trained psychologists at pre-training, after intensive training block, mid-placement and post-placement. A consent form will be sent to the training participant to authorise the use of data for analysis. Repeated measures design will be adopted for this study.

Repeated measures design will be adopted for this study. Individual guided self-help LIACT service, eligible participants will receive 6-8 sessions of guided self-help LIACT over three to four months. Clinical outcomes (depression and anxiety levels) will be measured at every session, it will take around 5 minutes to complete these two routine outcome measures. Other primary and secondary outcome measures, including general well-being, functioning and activity impairment, psychological flexibility, experiential avoidance, and therapeutic alliance will be at 3 time points, namely pre-treatment, post-treatment (at the end of the last session) and 6-week follow-up. Participants will take around 20 minutes to complete the full package of assessments. These outcome variables will be additionally measured after each

session to avoid missing data if participants drop out. Recovery rate and reliable improvement rate will also be used as indicators to evaluate the efficacy of LIACT. Focus groups will be conducted on participants who drop out and complete the programme to understand their experience and journey.

Curriculum

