6. Therapeutic alliance: The Working Alliance Inventory (WAI) was developed by Horvath and Greenberg in 1989. The brief revised version (Brief Revised Working Alliance Inventory; BR-WAI) consists of 12 items available multilingually (including Chinese). The scale is rated on a 5-point Likert scale, ranging from 1 (never) to 5 (always).
7. Experiential avoidance: The Brief Experiential Avoidance Questionnaire (BEAQ; Gámez et. al., 2014) is a shortened 15-item self-report measure designed to assess experiential avoidance, or the avoidance of uncomfortable or distressing thoughts and emotions. These statements are scored on a scale ranging from 1 (strongly agree) to 6 (strongly disagree).
8. Work Productivity and Activity Impairment: Work Productivity and Activity Impairment Questionnaire: General Health (WPAI) was developed by Reilly et. al. (1993) to measure impairments in both paid work and daily activities due to health-related problems. The domains covered include work time missed, impairment at work, productivity loss and activity impairment.

9.

Data analyses

For individual service, only the data of participants who have attended two or more follow-up sessions will be included for analysis. The first assessment session will not be counted for this requirement. Firstly, inter-correlations among all outcome measures will be assessed with Pearson's correlation coefficients. Secondly, the changes in outcome variables between pre-treatment, post-treatment and 3-month follow-up will be evaluated with repeated measures ANOVA. Cohen's *d* will be calculated to assess the relative effect sizes. Furthermore, reliable significant improvement will be computed according to the method recommended by Jacobson & Truax (1991), which is the division of pre-post treatment score difference by the standard error.

Compliance

The protocol of this study complies with the Declaration of Helsinki, IGH-GCP and research ethics principles to protect the rights, safety and well-being of participants.

References

doi:10.1111/j.1600-0047.2004.00329.x

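### Two separate selection steps decide who is counted: a two-session filter on every individual-service analysis, and a three-time-point ANOVA with no method for missing scores

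*Combined protocol and SAP*

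**What the plan says.** The Data analyses section sets the analysis population for individual service first: "only the data of participants who have attended two or more follow-up sessions will be included for analysis". It adds: "The first assessment session will not be counted for this requirement". I therefore read the required sessions as intervention sessions after assessment. The rule precedes, and so covers, the correlations, the ANOVA, Cohen's d and the reliable improvement index.

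The analysis of change follows: "the changes in outcome variables between pre-treatment, post-treatment and 3-month follow-up will be evaluated with repeated measures ANOVA". The section mentions no imputation, carry-forward rule, mixed model or other treatment of incomplete records.

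The Research design section bears on this in three ways:
- Depression and anxiety are routine measures at every session. The other outcomes are taken additionally after each "session to avoid missing data if participants drop out".
- The later assessments are "post-treatment (at the end of the last session) and 6-week follow-up". The Aims section instead has questionnaires "pre-intervention, during each session, and at a three-month follow-up", and the Data analyses section also says three months.
- "Recovery rate and reliable improvement rate will also be used as indicators to evaluate the efficacy of LIACT".

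**The concern.** The study has one treated group and no control, so the mean change among the people counted is itself the evidence for the hypothesis. Who is counted therefore matters directly. Two rules narrow that group after treatment has begun, and each can act on people whose response differs from the rest.

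Drop-out was foreseen, and participants carry the burden of repeated questionnaires partly because of it. Yet the analysis section gives the session scores no role, and no result is planned for everyone who began the intervention. At stake are the reported mean changes, any effect size taken from the ANOVA, and the recovery and reliable improvement rates by which efficacy will be judged.

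**Working it through.** **1. There is no planned figure to reproduce.** The only number is 300 people for initial screening. The documents give no expected number of starters, attendance rate, follow-up rate or drop-out allowance.

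**2. Does the ANOVA lose people without follow-up?** In standard form it needs a score in each of the three cells. As a check, one cell was removed from a made-up data set of 20 people at 3 times. A standard routine (AnovaRM in statsmodels) refused the data as unbalanced. An incomplete person must be removed or the cell filled, and the plan names no way to fill it.

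- Post-treatment cell: this is defined as the end of the last session, so a leaver's last attended score may fill it.
- Follow-up cell: no session score is taken after treatment ends, so nothing fills it.

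**3. Which step reaches which analysis?**

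| Analysis | Two-session filter | Follow-up score needed |
|---|---|---|
| ANOVA and its pre-post contrast | yes | yes, in standard form |
| Cohen's d | yes | not stated; yes if taken from the ANOVA |
| Reliable improvement | yes | no, uses pre and post only |
| Recovery rate | yes | not stated |

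**4. Numbers lost.** Let f be the share of starters who fail the filter and m the share of the rest with no follow-up score. Out of N starters, the filter removes N·f and the ANOVA a further N·(1−f)·m. The filter removes more when f > (1−f)·m, that is, when f > m/(1+m). For m = 0.30 the threshold is 0.30/1.30 = 23%; for m = 0.50 it is 0.50/1.50 = 33%. Treating all 300 as starters (an assumption, since 300 is the screening figure):
- f = 0.20, m = 0.30: 60 lost, then 240 × 0.30 = 72, leaving 168.
- f = 0.30, m = 0.20: 90 lost, then 210 × 0.20 = 42, leaving 168.

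Over f = 0.10, 0.20, 0.30, 0.40 crossed with m = 0.10 to 0.50 in steps of 0.10, the filter is the larger loss in 12 of 20 combinations.

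**5. Mean improvement.** Let a, b and c be the mean improvement, in scale points, of filter-failers, of filter-passers without follow-up, and of complete cases.
- Two-session set: T = m·b + (1−m)·c
- All starters: A = f·a + (1−f)·T
- ANOVA set: c

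All inputs below are assumed.

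| f, m | a / b / c | A | T | ANOVA | Filter adds | ANOVA adds |
|---|---|---|---|---|---|---|
| 0.20, 0.30 | 0 / 3 / 5 | 0.80 × 4.40 = 3.52 | 0.9 + 3.5 = 4.40 | 5.00 | 0.88 | 0.60 |
| 0.10, 0.40 | 1 / 3 / 5 | 0.1 + 3.78 = 3.88 | 1.2 + 3.0 = 4.20 | 5.00 | 0.32 | 0.80 |

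The filter matters more in the first row and the ANOVA in the second.

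**6. The sign can also turn.** Take the first row and exchange b and c, so that those without follow-up improved by 5 points and complete cases by 3. Then T = 1.5 + 2.1 = 3.60 and the ANOVA gives 3.00, which is 0.60 too small for the two-session set.

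**The case against.** - **The filter is a legitimate choice.** The Introduction cites a UK evaluation whose recovery rate also refers to people with two or more sessions, and the hypothesis is about change in people who have had treatment ("It is hypothesised that after receiving the low-intensity psychological intervention"). This stands as a reason to report the two-session set. It does not justify having no all-starters result beside it. Exact comparability with the cited rate cannot be claimed either, because the Introduction does not say how sessions were counted there.
- **Listwise deletion is not written in the plan.** This is correct: it is inferred from the usual form of the method. What is certain is that no alternative is named.
- **The drop-out data have a stated purpose.** That is true for the outcomes measured additionally after each session; depression and anxiety are routine every-session measures. Only the analysis rule is absent, and defining post-treatment as the end of the last session goes some way for that time point.
- **A mixed model brings its own assumptions.** It does. It needs a time course that covers both treatment and follow-up, and it is valid only if missingness depends on recorded scores.

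A reader might infer that the attendance filter is minor beside the ANOVA. The documents give no attendance or follow-up rates, and the order reverses within the assumed ranges above. The filter is also the rule actually written down, and the one that reaches reliable improvement. A reader might equally infer that the plan inflates the benefit. That needs poor responders to be the ones lost, which the documents do not show.

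**Conclusion.** The concern holds as two separate selection steps, both worth correcting. Neither can be ranked above the other from the documents. The filter affects every individual-service analysis. The ANOVA, in standard form, affects its own contrasts and any effect size taken from it, but not reliable improvement. Correcting one leaves the other in place: a model that accepts incomplete records does not bring back early leavers while the filter stands, and lifting the filter does not bring back people without follow-up while the ANOVA stands.

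Size and sign are unknown. In the two main illustrations the ANOVA set exceeds all starters by 5.00 − 3.52 = 1.48 points and 5.00 − 3.88 = 1.12 points, but these rest wholly on assumed rates and responses in which poor responders are lost. This is a cheap improvement to the plan and does not show that its results will be wrong in a given direction.

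**What to change.** 1. Make the main analysis set everyone who attends at least one LIACT session after assessment and has a pre-treatment score.
2. Replace the ANOVA with a likelihood-based linear mixed model using all pre-treatment, session, post-treatment and follow-up scores. Model time flexibly enough to span treatment and follow-up, and give pre-post and pre-follow-up contrasts at stated times.
3. State the missing-at-random assumption, and add one sensitivity analysis in which unseen scores are worse than predicted.
4. Report reliable improvement over all starters, with a stated rule for missing post-treatment scores.
5. Keep the two-or-more-sessions set as a labelled secondary analysis.
6. Reconcile the six-week and three-month follow-up statements before fixing the follow-up contrast, since they decide which score counts as missing.

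The cost is a reworded analysis section and slightly more analysis work, with no new data. Headline figures may be less favourable. Bias remains if people leave for reasons that their recorded scores do not reflect.

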LICBT is a disorder-specific intervention, it adopts different CBT intervention strategies for different presenting problems, for example, behavioural activation for depression, worry time and problem solving for generalised anxiety, and exposure and habituation for panic and phobia. Transdiagnostic intervention has been gaining evidence over the past decade to target the underlying psychological mechanism and thus treat different presenting problems with the same set of strategies. Acceptance and commitment therapy (ACT) is one of the well-researched intervention approaches. Meta-analysis showed that ACT can effectively reduce the level of depression and anxiety, while brief ACT approach also showed promising results (Bai, Luo, Zhang, Wu, & Chi, 2020; Haller, Breilmann, Schröter, Dobos, & Cramer, 2021; Kyllönen, Muotka, Puolakanaho, Astikainen, Keinonen, & Lappalainen, 2018).

Mental Health in Hong Kong

Due to the huge success of the IAPT programme, its concept is worth borrowing and applying to Hong Kong. Mind Mental Health Hong Kong (Mind HK) has launched a programme named Improving Access to Community Therapies, or ‘iACT’ for short. iACT was developed in accordance with the IAPT programme and incorporated the principles of low-intensity psychological intervention and ACT principles. In this programme, Mind HK will train 30 bachelor’s degree holders to study a low-intensity psychological intervention programme. The study programme consists of 120 hours of intensive training and a 9-month placement in community settings, including non-government organisations, schools, and private clinics. The trained psychological well-being practitioners (PWPs) will provide low-intensity acceptance and commitment therapy (LIACT) to around 300 adults who are screened with mild to severe depressive or anxiety symptoms without imminent risk.

Individuals will later receive LIACT offered by PWPs and complete guided self-help workbooks with guidance. PWPs will be trained and supervised for providing LIACT. In addition to the 120-hour training, they received regular supervision from recognised supervisors, including clinical psychologists, social workers, and experienced counsellors. Aspects of case management and clinical skills will be covered during supervision. Despite the promising results of the IAPT programme, the effectiveness of LIACT in a local context has yet been examined.

Aims of the study

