Individuals with depression or anxiety symptoms will be sampled in this study. Participants will be recruited from the placement organisations and promotions on social media, web pages, and at mental health centres. The sample size is estimated to be 300 individuals for initial screening for LIACT-guided self-help services.

Inclusion criteria

1. Adults aged 18-65
2. Adults with a specific set of presenting problems
3. Anxiety problems (including social, generalised, health anxiety, work anxiety)
4. Mild to moderate depression
5. Other emotional challenges include (but not limited to): Low self-esteem, perfectionism, mild anger issues, interpersonal or relational challenges, low motivation, lack of purpose, and numbness

Exclusion criteria

1. Adults with the following features/presentations are not eligible for the PWP programme and should automatically lead to an onward referral:
2. High severity on depressive score (PHQ9 \geq 20)

3. High or imminent risk (according to scores on PHQ9 question no. 9 and information emerging at triage assessment, including indication of plan and action or the lack of protective factor)
4. Any of the following presentations or situations: diagnosis or features of a mental health problem that is not suitable for low-intensity intervention, obsessive compulsive disorder, post-traumatic stress disorder, bipolar disorder, schizophrenia and other psychotic disorders, dissociative disorders, personality disorders, eating disorders, gender dysphoria, paraphilic disorders, anger issues as primary presenting concern (without anxiety or depression), sleep issues as primary presenting concern (without anxiety or depression), psychotic experiences (e.g. hallucinations), substance-related disorders, history of trauma or abuse that is considered highly relevant to the current presenting problem they are seeking support for, planned changes to psychotropic medication during the period of PWP intervention, currently receiving regular psychological counselling or support from another practitioner for at least twice a month, diagnosis of a learning disability, cognitive impairment or neurodevelopmental condition that would impair their ability to engage with a structured, manualised intervention (e.g. untreated ADHD or moderate-severe brain injury), clear safeguarding concerns requiring multi-agency support (e.g. concerns about domestic abuse)

Research design

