The LIACT training curriculum is designed by registered clinical psychologists with consultation from local ACT experts from the Association of Contextual and Behavioural Science (Hong Kong Chapter). There are 5 modules in the intensive training block including introduction, professional and ethics issues, application of ACT low-intensity intervention, troubleshooting and preparation for clinical placement. The LIACT protocol is also piloted and revised by clinical psychologists to ensure its adaptability to local situations. After 120 hours of intensive training, the training participants will attend a role-play exam to ensure their competency to proceed with the 9-month placement. During the 9-month placement, each PWP is expected to see at least 15 direct service beneficiaries to provide LIACT. During which, supervision will be provided regularly to ensure the quality of service delivery and risk management. There will be a mid-placement review and final placement review, and the training participants will submit audio recordings for supervisors to rate for their competence. Focus groups will be conducted for the training participants to understand their learning experience.

Treatment

Guided self-help LIACT will be provided to eligible participants. For individual guided self-help LIACT service, intake assessment will be conducted to assess the presenting problem of the participants at pre-treatment to ensure the suitability to receive LIACT service. Participants will be given the LIACT self-help workbook collaboratively with a PWP. Between each session, clients will read through the workbook and complete the exercises suggested in the workbook. In subsequent sessions, PWP will guide clients to overcome the difficulties in performing the LIACT exercises.

Therapists

PWPs will be responsible for providing LIACT to the participants. PWPs have completed a 120-hour intensive training and pass the role play examination prior to placement provision. The training was provided by experienced clinical psychologists and counsellors. Moreover, PWPs are under regular supervision by clinical psychologists, experienced counsellors, or social workers with extensive ACT training.

Outcome Measures

Training evaluation.

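### Thirty trainee practitioners treat the participants, but the planned repeated measures ANOVA has no practitioner term; if practitioners differ in the change they produce, its p-values are too small for conclusions beyond these 30

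*Combined protocol and SAP*

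**What the plan says.** The section Mental Health in Hong Kong gives the number of practitioners: "In this programme, Mind HK will train 30" degree holders. Once trained, they provide LIACT "to around 300 adults who are screened with mild to severe depressive or anxiety symptoms". Treatment and Therapists confirm that each participant works through the workbook with a practitioner, so participants are nested within practitioners. Curriculum adds a caseload: "each PWP is expected to see at least 15 direct service beneficiaries to provide LIACT".

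Aims of the study has two parts. The first is a "comprehensive evaluation of a training curriculum designed for teaching low-intensity psychological interventions". The second is to "examine the outcomes of low-intensity psychological interventions, delivered by the trainees, targeting adult individuals". The background section gives as a reason for the study that LIACT's effectiveness had not yet been studied locally.

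Under Data analyses, change from before treatment to after it and on to follow-up "will be evaluated with repeated measures ANOVA". The rest of the plan for service participants is Pearson correlations, Cohen's d and reliable change. Neither this section nor any other mentions a practitioner factor, a mixed or multilevel model, a clustered standard error or an ICC. Practitioner competence is rated repeatedly in the training part, but it is not linked to the participants' outcomes.

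**The concern.** The error term of a repeated measures ANOVA is the participant-by-time variation, with participants taken as independent. A practitioner whose participants all start or stay somewhat higher does no harm, because a constant shift cancels within each participant. A practitioner whose participants improve more, or less, than others do is different. That practitioner-by-time component is shared by everyone the practitioner treats, so it does not average out over participants as quickly as the error term assumes.

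This matters when the result is read as what practitioners trained this way achieve. For an evaluation of a curriculum and of LIACT in Hong Kong, that is the question the background raises. On that reading the p-values are too small, and any interval given for mean change is too narrow. Point estimates and individual reliable-change classifications are unaffected.

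**Working it through.** **Inputs from the documents.** There are 30 practitioners and about 300 participants (Mental Health in Hong Kong), so 300/30 = 10 each. Curriculum gives at least 15 each. The analysis set drops anyone with fewer than two follow-up sessions, and no dropout rate is stated.

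**Assumed, because the documents give no value.** The test is at two-sided 0.05. The ICC of change (the practitioner-by-time share of the participant-by-time variance) is 0, 0.02, 0.05 or 0.10. The number analysed per practitioner, m, is 5 (heavy attrition), 10 or 15. Caseloads are equal and data complete. The plan has no power calculation or interval of its own to reproduce.

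**Type I error.** The design effect is DEFF = 1 + (m − 1) × ICC. With three time points the F test has 2 numerator df and a large error df, so F behaves as a chi-square on 2 df divided by 2. Its upper tail is exponential, and clustering scales the numerator by DEFF. Hence true type I error = 0.05^(1/DEFF). For m = 10 and ICC 0.05, DEFF = 1 + 9 × 0.05 = 1.45 and 0.05^(1/1.45) = 0.127.

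| m | ICC | DEFF | Type I error of nominal 0.05 ANOVA |
|---|---|---|---|
| 5 | 0.02 | 1.08 | 0.062 |
| 5 | 0.05 | 1.20 | 0.082 |
| 5 | 0.10 | 1.40 | 0.118 |
| 10 | 0.02 | 1.18 | 0.079 |
| 10 | 0.05 | 1.45 | 0.127 |
| 10 | 0.10 | 1.90 | 0.207 |
| 15 | 0.02 | 1.28 | 0.096 |
| 15 | 0.05 | 1.70 | 0.172 |
| 15 | 0.10 | 2.40 | 0.287 |

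At ICC 0 every row returns 0.05.

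**Simulation check.** With 30 practitioners, no true mean change and 10,000 runs per setting, the planned ANOVA rejected in 0.053, 0.129 and 0.206 of runs at m = 10 (ICC 0, 0.05, 0.10), and in 0.048, 0.167 and 0.282 at m = 15. The same ANOVA on the 30 practitioner means rejected in 0.050 to 0.053. The inflation therefore comes from ignoring the practitioner.

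**Interval for mean pre-post change, if one is reported.** Half-width in SDs of change is t(n − 1)/√n if participants are independent, and t(29) × √(DEFF/n) allowing for practitioner. With n = 300 these are 1.968/17.32 = 0.114 against 0.128, 0.142 and 0.163 for ICC 0.02, 0.05 and 0.10. A nominal 95% interval that ignores practitioner then covers about 93%, 90% and 84%.

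**Cost of the change in df alone (ICC 0).** t(29)/t(n − 1) is 2.045/1.976 = 1.035 at n = 150, 2.045/1.968 = 1.039 at n = 300 and 2.045/1.965 = 1.041 at n = 450. Intervals are about 4% wider.

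**When a conclusion would move.** For a mean change of 0.15 SD with n = 300, t = 0.15 × 17.32 = 2.60 and the unadjusted p is 0.010. Dividing t by √1.45 or √1.90 and using 29 df gives p = 0.039 (ICC 0.05) or 0.070 (ICC 0.10). For a change of 1.41 SD, a pre-post effect size cited in the introduction from another study and taken here in SDs of change, p is below 1e-16 either way.

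**The case against.** The strongest reply has four parts.

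First, no target of inference is formally stated. If the study only describes what these 30 trainees achieved, the stated problem disappears. This stands as a condition, and the sponsor may choose that reading. The background nevertheless frames the question as whether LIACT works locally, which reaches beyond 30 people.

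Second, the size rests on an assumed ICC. A common workbook, an entry role-play examination and regular supervision may well make practitioners alike. At ICC 0.02 with 5 analysed each, type I error is only 0.06. That also stands. It is a reason to estimate the variance rather than to leave it out without comment.

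Third, effects may be so large that nothing changes. For large effects this is right. The plan lists eight service measures, however, and gives no reason to expect a large change on all of them.

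Fourth, there is one treated group and no control, so rejecting zero change is weak evidence of effectiveness whatever the error term. This is true, and the fix does not repair it. Nor would a practitioner term fully cover clustering by placement site or supervisor.

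A reader might infer more than the documents support in three ways. One is that the significance findings will be invalid; with no ICC given and ICC zero possible, that cannot be said. Another is that the planned rates carry intervals that are too narrow. Research design does say "Recovery rate and reliable improvement rate will also be used as indicators to evaluate the efficacy of LIACT", but Data analyses plans no interval for a rate, so this applies only if one is reported. The third is to count the sample size figures as part of this point. Service Participants says "The sample size is estimated to be 300 individuals for initial screening for LIACT-guided self-help services", while 30 × 15 = 450. That is a separate matter to clarify; here it only makes the cluster size uncertain.

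**Conclusion.** The point holds conditionally. The nesting is clear from the documents and the analysis section has no practitioner term. If practitioners differ in the change they produce, and conclusions are meant to reach practitioners trained this way, the planned p-values are too small. Over the assumed range of ICC up to 0.10 and 5 to 15 analysed per practitioner, the true type I error of the nominal 0.05 test runs from 0.05 (ICC 0) to 0.29. These figures assume equal caseloads and complete data. No main conclusion is shown to be at risk: the exposure is in stated precision and in outcomes whose change is small. This is a low-cost improvement to the analysis plan.

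**What to change.** In Data analyses, replace the ANOVA with a linear mixed model for the repeated scores, with participant effects and a practitioner random effect on time, using small-sample degrees of freedom. A practitioner random intercept alone would not address the problem. Name practitioner-clustered standard errors with a small-sample correction (about 30 clusters) as the fallback if the model does not converge. Report the practitioner ICC of change. If an interval is given for an improvement or recovery rate, cluster it by practitioner as well. If inference is meant only for these 30 trainees, say so instead.

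The cost is SAP wording, a practitioner identifier in the analysis file and a more complex model, which may be hard to fit when practitioner variance is near zero. Intervals would be about 4% wider even if that variance is zero. No extra participants or assessments are needed.
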